10.2 Clinical Laboratory Evaluation

Collection of blood and urine specimens for haematology (including full blood counts, differential and platelet count), biochemistry (including creatinine, Aspartate Aminotransferase [AST] and Alanine Aminotransferase [ALT]) and urinalysis tests (urine dipstick analysis and urine microscopy if clinically indicated) is conducted at Screening or any other trial visit if clinically indicated. For the South African research centres, clinical laboratory assessments are performed by a central laboratory, and for the Uganda research centre, by the research centre's certified laboratory. In accordance, reference ranges are provided by the central laboratory and local laboratory, respectively.

Listings of all clinical laboratory data for each participant will be provided. Laboratory test results will be categorised by DAIDS Grade, and clinical significance. Specific haematology, biochemistry, urinalysis, and microscopy parameters assessed during the trial are listed below.

Table 5 Haematology, Biochemistry, Urinalysis and Microscopy Parameters

Haematology (continuous) ¹	Biochemistry (continuous) ¹	Urinalysis (continuous)
Erythrocytes	Electrolytes	N/A
Haemoglobin	Sodium	
Haematocrit	Potassium	
Platelets	Chloride	
Leukocytes	Calcium	
Neutrophils	Phosphate	
Lymphocytes	Liver Function	
Monocytes	Bilirubin	
Eosinophils	Alkaline phosphatase	
Basophils	ALT	
	AST	
	Renal Function	
	Urea	

¹ Graded according to the DAIDS table¹ (Grades 1-4).

Haematology (continuous) ¹	Biochemistry (continuous) ¹	Urinalysis (continuous)
	Creatinine	

Data sources: Haematology and biochemistry reported in HAE and CHEM CRFs; urinalysis and microscopy reported in UTR CRF.

Additionally, a listing of all abnormal clinical laboratory data will be provided.

10.3 Pelvic examinations

10.3.1 Assessments

Pelvic examinations will be performed at Screening and the last product use visit, or at any visit if clinically indicated.

10.3.2 Summary Tables

A summary of pelvic examinations will be presented for the all scheduled trial visits, overall, IPM 027 treatment arm and by research centre in tabular form. By-participant listings will also be provided. The summary tables and listings will include the variables in Table 6 below.

Table 6 Pelvic Examination Variables

Variable	Data Type	Data Sources
Presence of Vulvar findings	Categorical	Source: PEL Indicator variable for: Vulvar erythema, vulvar edema, vulvar rash, vulvar tenderness, Bartholin's or Skene's gland abnormality
Presence of Vaginal findings	Categorical	Source: PEL Indicator variable for: Vaginal erythema, vaginal edema, vaginal masses, vaginal abrasions or lacerations, vaginal tenderness, vaginal discharge
Presence of Cervical findings	Categorical	Source: PEL Indicator variable for: Cervical erythema, cervical edema and/or friability, cervical masses, cervical motion tenderness, cervical discharge
General/other findings	Categorical	Source: PEL Indicator variable for: Odour, uterine masses, adnexal masses, uterine tenderness, adnexal tenderness, condyloma, abnormal genital tract bleeding, other
Presence of Vulvar Lesions findings	Categorical	Source: PEL Indicator variable for: Ulcer, blister, pustule, peeling, ecchymosis, other lesions
Presence of Vaginal Lesions findings	Categorical	Source: PEL Indicator variable for: Ulcer, blister, pustule, peeling, ecchymosis, other lesions
Presence of Cervical Lesions findings	Categorical	Source: PEL Indicator variable for: Ulcer, blister, pustule, peeling, ecchymosis, other lesions
Cervical ectopy	Categorical	Source: PEL

10.4 Cervical cytology

10.4.1 Assessments

A cervical cytology sample will be collected at Screening (if not done in the previous year or if the result was abnormal at the last point of testing) and as needed.

10.4.2 Summary Tables

A summary of the cervical cytology results will be presented overall, IPM 027 treatment arm and by research centre, for the Screening visit. By-participant listings will also be provided for all visits. The summary tables and listings will include the following variables:

Table 7 Cervical Cytology Variables

Variable	Data Type	Data Sources
Cervical cytology result	Categorical	Source: CR Indicator variable for: Negative for intraepithelial lesion or cancer (malignancy), ASCUS, SIL-low grade (LSIL), ASC-H, SIL-high grade (HSIL), AGC, AGC-favor neoplastic, cancer, other findings

10.5 STI assessments

10.5.1 Assessments

Cervicovaginal samples will be collected for STI testing (Trichomonas, Gonorrhoea, and Chlamydia) at Screening and at the last product use visit, or any other trial visit as clinically indicated. At Screening, blood will be collected for Syphilis (RPR) testing. TPHA/TPPA testing will be performed if the RPR is reactive.

10.5.2 Summary Tables

STI results will be presented for the Screening and last product use visits, overall, IPM 027 treatment arm and by research centre. Variables that will be summarised in the tables and listings include:

Table 8 STI Variables

Variable	Data Type	Data Sources
Trichomonas rapid Test	Dichotomous	Source: STI
Gonorrhoea	Dichotomous	Source: STI
Chlamydia	Dichotomous	Source: STI
Syphilis RPR screening test	Dichotomous	Source: STI
Syphilis RPR titre	Discrete	Source: STI
Syphilis confirmatory test TPHA/TPPA	Categorical	Source: STI
Blood present during collection of cervico-vaginal samples	Dichotomous	Source: STI

10.6 Immediately Reportable Events

In addition to SAEs, the following events are considered immediately reportable events (IREs):

- 1) Pregnancy
- 2) HIV-1 seroconversion
- 3) Any non-serious AE leading to permanent discontinuation of the IP

10.6.1 Assessments

Urine pregnancy tests will be conducted at all scheduled trial visits, except for the Exit visit, and can be performed additionally at unscheduled visits as needed. Serum pregnancy tests will be performed at the Investigator's discretion. A negative serum test after a positive urine test would overrule the positive urine test.

HIV rapid tests will be performed at the research centre at all trial visits until the last product use visit, and at the exit visit, 1-2 months after ring discontinuation, and as needed. HIV RNA PCR samples will be collected at the Screening and Enrollment visits and at all trial visits, but will only be analysed if there is reason to believe that the participant is HIV-positive.

All AEs (serious and non-serious) are monitored throughout the trial; analysis of AEs is discussed in Section 10.1.

10.6.2 Summary Tables

Results from pregnancy tests will be presented in tabular form overall, by IPM 027 treatment arm and by research centre for each trial visit and will include appropriate statistics. A table including the following summaries will be included:

- Proportion of pregnancies
- Pregnancy incidence rates by contraceptive method (DMPA, norethisterone, oral contraception, etc.)
- Pregnancy incidence rates by outcome (full term live birth, premature term live birth, etc.).
- Pregnancy incidence rates per 100 person-years
- Frequencies of congenital anomalies

By-participant listings will be provided for each participant.

Table 9 Pregnancy Tests

Variable	Data Type	Data Sources
Type of test (urine or serum)	Dichotomous	Source: PHTR

Pregnancy Test	Dichotomous	Source: PHTR
----------------	-------------	--------------

Results from HIV tests will be presented in tabular form overall, by IPM 027 treatment arm and by research centre for each trial visit and will include appropriate statistics. By-participant listings will be provided for each participant, including whether the participant HIV-1 seroconverted (confirmed), the date of seroconversion, the time to seroconversion, and whether HIV-1 infection occurred while using IP.

Table 10 HIV Tests

Variable	Data Type	Data Sources
HIV Test Result (Test #1)	Dichotomous	Source: PHTR
HIV Test Result (Test #2)	Dichotomous	Source: PHTR
HIV Test Result (Test #3)	Dichotomous	Source: PHTR
HIV-1 Western Blot	Nominal	Source: SER
Repeat HIV-1 Western Blot	Nominal	Source: SER
HIV-2 Western Blot	Nominal	Source: SER
Repeat HIV-2 Western Blot	Nominal	Source: SER
RNA PCR Testing	Nominal	Source: electronic lab data *Only tested for HIV-1 seroconverters

10.7 Concomitant Medications

Concomitant medication is defined as any medication taken in conjunction with the IP, *i.e.* medication that either:

- 1) Started after the first insertion of the IP, or
- 2) Started before the first insertion of the IP, but ended on or after the first insertion of the IP. This includes medication indicated as “Ongoing” at the end of the trial.

Concomitant medications will be coded using the WHO DDE (version June 2017); a table displaying the frequency and proportion of participants using medications during the trial overall, by research centre, and by ATC level 2 and preferred name, will be presented. Concomitant medication will also be presented in the form of listings which will contain information for each medication used.

Table 11 Concomitant Medication Variables

Variable	Data Type	Data Sources
Drug Name	Text	Verbatim; Source: CM, CMTRT_1-3
ATC category	Text	Verbatim; Source: CM, ATCCODE1-3
Indication	Text	Verbatim; Source: CM, CMINDC_1-3
Dose/Unit	Text	Verbatim; Source: CM, CMDOSE_1-3
Route	Text	Verbatim; Source: CM, CMRTE_1-3
Frequency	Text	Verbatim; Source: CM, CMDSFQ_1-3

Start date	DDMMYY	Source: CM, CMSTD _T _1-3
Stop date	DDMMYY	Source: CM, CMEND _T _1-3
Ongoing at last visit	Dichotomous	Source: CM, CMONGO_1-3

10.8 Physical Examination Findings and Vital Signs

A physical examination will be conducted at Screening and at the last product use visit. At these visits, vital signs will be recorded and body systems will be evaluated for abnormal/normal findings, with the exception of Height, which will only be measured at Screening. For vital signs, the observed data and the absolute change from baseline (Screening) will be summarised overall and by research centre using appropriate descriptive statistics, as described in Section 6.6. Listings of all vital signs data will be provided.

Data from physical examination findings will be listed only.

Variables that will be summarised in the listings include:

Table 12 Physical Examination and Vital Signs Parameters

Variable	Data Type	Data Sources
Height	Continuous	Source: PX (Screening)
Weight	Continuous	Source: PX
BMI	Continuous	Derived: weight(kg)/height(m) ² , rounded to 1 decimal
Temperature	Continuous; Dichotomous	Source: PX
Pulse	Continuous; Dichotomous	Source: PX
Respiratory rate	Continuous; Dichotomous	Source: PX
Blood pressure	Continuous; Dichotomous	Source: PX
General Examination of Body Systems: General appearance, gastrointestinal/abdomen, neck, lymph nodes, cardiovascular/heart, respiratory/lungs, musculoskeletal/extremities, neurological, skin, eyes, ear/nose/throat, and other (1-3).	Nominal	Source: PX

10.9 Social Harms

During each HIV counselling session, participants will be asked questions to assess the occurrence of social harms related to trial participation. Participants who experience social harms related to trial participation will be counselled accordingly and

provided with assistance to mitigate the circumstances, if possible. This will be recorded in the source documents and applicable CRFs.

By-participant listings of all social harms data will be provided as well as summary tables of such occurrences. Social harms that were reported as AEs, as well as all occurrences of sexual assault (whether associated with physical injury or not), will be summarised by SOC and PT, and by severity (refer to Section 10.1).

11 CHANGES IN THE PROTOCOL-PLANNED ANALYSES

There are no changes to the protocol-planned analyses.

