8.4. Statistical Analyses

The primary analysis will focus on safety as well as adherence assessments.

The primary analysis will be performed under the intent-to-treat (ITT) principle, which will include all participants enrolled in the trial. As it is possible that the inclusion of non-adherent participants or participants who discontinued from the IP may artificially lower the rates of safety outcomes, additional analyses will be conducted on the per-protocol population, which will include only participants who were adherent to the protocol. Details on the definition of the per-protocol population, in addition to models that will be

used to examine the exploratory objectives and other technical aspects of these analyses will be provided in a SAP, which will be finalised prior to final database lock.

The analysis of the secondary safety assessments will be mainly descriptive in nature. The incidence density rate of HIV-1 seroconversion and the frequency of HIV-1 drug resistance in women who seroconvert will be summarised descriptively.

The data will be presented using appropriate statistical measures including, but not limited to: mean, standard deviation, median, and interquartile range for continuous data; frequency and relative frequency for categorical data. When appropriate, 95% confidence intervals will be presented.

8.4.1. *Primary Safety Analysis*

A descriptive analysis of all AEs will be presented in tables and listings. AEs will be summarised by MedDRA System Organ Class (SOC) and Preferred term (PT). The proportion of participants experiencing adverse events, including the proportion of participants experiencing product-related adverse events, Grade 3 or 4 AEs, or SAEs, will be determined, and presented with corresponding 95% CIs.

All data will be presented by research centre, and overall across research centres.

8.4.2. *Primary Adherence Analysis*

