Residual levels of dapivirine in returned rings and/or plasma and/or vaginal fluid concentrations of dapivirine will be used as measures of adherence to ring use. The data will be listed, summarised and presented graphically. Participants will be categorized as either adherent or non-adherent, based on these measures. The ring residual levels and/or plasma and/or vaginal fluid concentrations of dapivirine associated with non-adherence will be informed by the results from IPM 027, and will be described in detail in the SAP, which will be finalised prior to final database lock. The correlation between the amount of residual dapivirine in the used rings and the corresponding plasma and/or vaginal fluid levels of dapivirine will be explored graphically and summarised descriptively.

8.4.3. *Secondary Analyses*

8.4.3.1. *Incidence of HIV-1 seroconversion*

The incidence of HIV-1 seroconversions, the incidence density rate of HIV-1 seroconversion, i.e. HIV-1 seroconversion rate per 100 woman-years of product use at the end of the ring use period, as well as a 95% CI for the HIV-1 seroconversion rate per 100 woman-years based on the normal approximation of the Poisson distribution will be presented for each research centre, and overall. Kaplan-Meier curves will be presented, stratified by research centre.

8.4.3.2. *HIV-1 drug resistance*

The analysis of HIV-1 drug resistance will be primarily descriptive in nature, and will depend on the pattern of resistance mutations observed in the HIV-1 seroconverters. The resistance associated mutations observed will be listed by participant, and a frequency tabulation of individual resistance mutations associated with the various

classes of antiretrovirals, e.g. Protease Inhibitors, Nucleoside Reverse Transcriptase Inhibitors and Non-nucleoside Reverse Transcriptase Inhibitors, will be produced. The proportion of HIV-1 seroconverters with at least one HIV-1 drug resistant mutation will be presented, with the corresponding 95% CI.

8.4.4. *Interim Analysis*

No interim analysis is planned for this trial. However, the Sponsor will review the treatment emergent safety data at regular intervals during the conduct of the trial.

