5.3 Per-Protocol (PP) Population

The PP (or protocol-adherent) population is a subset of the m-ITT population, *i.e.* all trial participants who are confirmed as HIV-1 negative at the enrollment visit, with no major protocol deviations, as defined in Section 7.2.

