9.3 Secondary Endpoints

9.3.1 Secondary Endpoint 1: HIV-1 seroconversion rate per 100 person-years of product use

Consistent with secondary objective 1, secondary endpoint 1 is the HIV-1 seroconversion rate per 100 person-years of product use at the end of the vaginal ring use period.

Assessments

Trial participants will be tested for HIV-1 infection at all trial visits until the last product use visit, and at the exit visit, 1-2 months after ring discontinuation. HIV-1 seroconversion will be determined per the HIV testing algorithm presented in the IPM 032 protocol (Appendix B) and assessed by the Principal investigator or dedicated sub-investigator at the research centre and the IPM clinical physician to confirm HIV-1 seroconversion and estimated point of infection⁵. The HSMC was established to act in advisory capacity as IPM 032 secondary endpoints did not require independent evaluation of HIV-1 seroconversions and/or HIV-1 trial endpoints. The HSMC was consulted on an ad hoc basis, e.g. regarding inconclusive or atypical HIV test results. The point of HIV-1 infection was estimated by performing reverse sequential HIV Ribonucleic Acid (RNA) Polymerase Chain Reaction (PCR) testing (on stored samples collected at each visit) until a negative test result is achieved.

Statistical methods

Participants who are not diagnosed with HIV-1 using seroconversion testing at the end of the trial participation period will be censored at the last HIV-1 test date, at or prior to the last product use visit.

If HIV-1 is detected at the Exit visit, HIV-1 RNA PCR testing will be performed on stored samples in reverse sequential order to estimate the time point of HIV-1 infection.

- If HIV-1 infection is detected at or prior to the last product use visit, the participant will be included in the analysis as an HIV-1 seroconverter.
- If the time of infection is determined to be after completion of product use, the participant will be censored on the last HIV-1 test date at or prior to the last product use visit.

This analysis (Analysis 1) will be performed on the m-ITT population, as well as on the PP population.

Three additional analyses of HIV-1 seroconversion rate will be performed:

- Analysis 2: In instances where it cannot be ruled out that HIV-1 infection may have occurred during IP use due to atypical/inconclusive HIV RNA PCR test results or extended periods of non-product use, such participants will be considered as HIV-1 infected on product in this analysis.

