		IPM 027 Dapivirine (N=XXX)	IPM 027 Placebo (N=XXX)	IPM 032 Overall (N=XXX)		IPM 027 Dapivirine (N=XXX)	IPM 027 Placebo (N=XXX)	IPM 032 Overall (N=XXX)
Any IP related TEAE	n (%) ^a 95% CI ^b	X (X.X) XX.X, XX.X	X (X.X) XX.X, XX.X	X (X.X) XX.X, XX.X	...	X (X.X) XX.X, XX.X	X (X.X) XX.X, XX.X	X (X.X) XX.X, XX.X
MedDRA System Organ Class 1	n (%) ^a	X (X.X)	X (X.X)	X (X.X)	...	X (X.X)	X (X.X)	X (X.X)
MedDRA Preferred Term 1	n (%) ^a	X (X.X)	X (X.X)	X (X.X)	...	X (X.X)	X (X.X)	X (X.X)
MedDRA Preferred Term 2	n (%) ^a	X (X.X)	X (X.X)	X (X.X)	...	X (X.X)	X (X.X)	X (X.X)
...								

Programmers Notes:

- Please repeat for each primary system organ class and preferred term
- Please repeat table for the following Subgroups: Age < 25 years; Age ≥ 25 years and IPM 027 participants who directly enrolled in IPM 032 (Note that the number of participants in the headers (N=XXX) should reflect the number of participants in each subgroup)

CI = Confidence interval; IP = Investigational product; TEAE = Treatment emergent adverse event

^a Percentages are calculated out of the number of participants in the safety population per centre and IPM 027 treatment

^b 95% CI are calculated using Fisher's exact test

System organ class and preferred term were coded using MedDRA (Version 19.0)

Centre 01: Madibeng Centre for Research (MCR); Centre 02: MatCH Research Unit (MRU); Centre 04: Qhakaza Mbokodo (QM);

Centre 06: MRC/UVRI & LSHTM Uganda Research Unit (MRC/UVRI); Centre 07: Desmond Tutu HIV Foundation (DTHF), Masiphumelele; Centre 08: Ndlovu Care Group (NCG)

Table 14.3.1.4
Grade 3 or 4 Treatment Emergent Adverse Events by System Organ Class and Preferred Term
Safety Population

Subgroup: All IPM 032 participants

MedDRA System Organ Class MedDRA Preferred Term	Statistic	Centre 01			...	All Centres		
		IPM 027 Dapivirine (N=XXX)	IPM 027 Placebo (N=XXX)	IPM 032 Overall (N=XXX)		IPM 027 Dapivirine (N=XXX)	IPM 027 Placebo (N=XXX)	IPM 032 Overall (N=XXX)
Any Grade 3 or Grade 4 TEAE	n (%) ^a 95% CI ^b	X (X.X) XX.X, XX.X	X (X.X) XX.X, XX.X	X (X.X) XX.X, XX.X	...	X (X.X) XX.X, XX.X	X (X.X) XX.X, XX.X	X (X.X) XX.X, XX.X
MedDRA System Organ Class 1	n (%) ^a	X (X.X)	X (X.X)	X (X.X)	...	X (X.X)	X (X.X)	X (X.X)
MedDRA Preferred Term 1	n (%) ^a	X (X.X)	X (X.X)	X (X.X)	...	X (X.X)	X (X.X)	X (X.X)
MedDRA Preferred Term 2	n (%) ^a	X (X.X)	X (X.X)	X (X.X)	...	X (X.X)	X (X.X)	X (X.X)
...								

Programmers Notes:

- Please repeat for each primary system organ class and preferred term

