Table 14.3.7.5

Analysis 1, HIV-1 Seroconversion Rate per 100 Person-Years of Product Use

Population: m-ITT

	Statistic	IPM 027 Dapivirine (N=XXX)	IPM 027 Placebo (N=XXX)	IPM 032 Overall (N=XXX)
Number of confirmed HIV-1 seroconversions on IP	n (%) ^a	X (X.X)	X (X.X)	X (X.X)
Total number of person-years	PY	XXX	XXX	XXX
Seroconversion rate (per 100 person-years)	n/PY	XX.X	XX.X	XX.X
95% CI for seroconversion-rate (per 100 person-years)	95% CI ^b	XX.X, XX.X	XX.X, XX.X	XX.X, XX.X

Programmers Note: Please repeat the table for the PP population

CI = Confidence interval; HIV-1 = Human immunodeficiency virus type 1; IP = Investigational product

^a Percentages are calculated out of the number of participants in the applicable population per IPM 027 treatment

^b 95% CI calculated as $[(n/PY) \pm 1.96 \times ([n/PY] / PY)^{1/2}] \times 100$; where n = number of HIV seroconversions and PY = total number of person-years of product use calculated as PY = (Date of last ring removal – Date of first ring insertion + 1)/365.25

Table 14.3.7.6
 Analysis 2, HIV-1 Seroconversion Rate per 100 Person-Years of Product Use
 m-ITT

	Statistic	IPM 027 Dapivirine (N=XXX)	IPM 027 Placebo (N=XXX)	IPM 032 Overall (N=XXX)
Number of confirmed HIV-1 seroconversions on IP	n (%) ^a	X (X.X)	X (X.X)	X (X.X)
Total number of person-years	PY	XXX	XXX	XXX
Seroconversion rate (per 100 person-years)	n/PY	XX.X	XX.X	XX.X
95% CI for seroconversion-rate (per 100 person-years)	95% CI ^b	XX.X, XX.X	XX.X, XX.X	XX.X, XX.X

CI = Confidence interval; HIV-1 = Human immunodeficiency virus type 1; IP = Investigational product

^a Percentages are calculated out of the number of participants in the m-ITT population per IPM 027 treatment

^b 95% CI calculated as $[(n/PY) \pm 1.96 \times ([n/PY] / PY)^{1/2}] \times 100$; where n = number of HIV seroconversions and PY = total number of person-years of product use calculated as PY = (Date of last ring removal – Date of first ring insertion + 1)/365.25

In instances where it cannot be ruled out that HIV-1 infection may have occurred during IP use in case the HIV RNA test has detectable levels at the next visit after ring use, such participants will be considered as being seroconverted

Table 14.3.7.7
 Analysis 3, HIV-1 Seroconversion Rate per 100 Person-Years of Product Use
 m-ITT

Statistic	IPM 027 Dapivirine (N=XXX)	IPM 027 Placebo (N=XXX)	IPM 032 Overall (N=XXX)
Number of confirmed HIV-1 seroconversions on IP	n (%) ^a	X (X.X)	X (X.X)

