Other	X (X.X)	X (X.X)	X (X.X)	X (X.X)	X (X.X)	X (X.X)	X (X.X)	X (X.X)	X (X.X)	... X (X.X)

Programmers Note: Please repeat the table for all available Trial Months

Percentages are calculated out of the number of participants in the safety population

IPM 032

FIGURE SHELLS – VERSION 1.0, 26 MAR 2020

Number	Listing Heading
14.1	Demographics
14.1.1.1	Disposition of Participants
14.1.1.1.1	Time to Trial Discontinuation
14.1.1.1.2	Time to (Premature) Permanent Investigational Product Discontinuation
14.3	Safety Data
14.3.5.1	Adherence – Dapivirine Residual Levels in Used Rings
14.3.5.1.1	Dapivirine Ring Residual Levels (mg)
14.3.5.1.2	Dapivirine Ring Residual Levels (mg) By Trial Visit and Category of Residual Amount
14.3.5.1.3	Relating The Dapivirine Ring Residual Levels (mg) To The Time Intervals Between Consecutive Ring Replacements
14.3.5.1.4	Residual Levels of Dapivirine (mg) in The Last Three Returned Rings Prior To HIV Seroconversion VS Average Ring Residual Levels
14.3.5.1.8	Corrected Residual Levels of Dapivirine in The Last Three Returned Rings Prior To HIV Seroconversion VS Average Ring Residual Levels of HIV- Participants
14.3.7	Other Safety Data
14.3.7.7	Time to HIV-1 Seroconversion – m-ITT population
14.3.7.8	Time to HIV-1 Seroconversion – PP population
14.6	Other Data
14.6.4	Correlation Between Dapivirine Residual Amounts (mg) in Returned Used Vaginal Rings and Results From Visual Inspection of Returned Vaginal Rings

Figure 14.1.1.1.1
Kaplan-Meier Curves, Time to Trial Discontinuity
Safety Population

[figure not shown]
[figure not shown]

Figure 14.1.1.1.2
Kaplan-Meier Curves, Time to (Premature) Permanent Investigational Product Discontinuation
Safety Population

[figure not shown]
Programmers Note: Figure wil resemble F14.1.1.1 with time to permanent IP data.

Figure 14.3.5.1.1
Dapivirine Ring Residual Levels (mg)
Safety Population

[figure not shown]
Programmers Note: Please repeat for all centres.

Figure 14.3.5.1.2
 Dapivirine Ring Residual Levels (mg) By Trial Visit and Category of Residual Amount
 Safety Population

Programmers Note: Please repeat for all trial months.

Figure 14.3.5.1.3
 Relating The Dapivirine Ring Residual Levels (mg) To The Time Intervals Between Consecutive Ring Replacements
 Safety Population

Programmers Note: Please repeat for all centres.

Figure 14.3.5.1.4
Residual Levels of Dapivirine (mg) in The Last Three Returned Rings Prior To HIV Seroconversion VS Average Ring Residual Levels
Safety Population

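### SAP Section 11 declares no change, but the planned per-protocol adverse-event analyses and the adherent/non-adherent classing of women are both missing from the SAP

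*SAP*

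**What the plan says.** **Protocol, safety.** Section 8.4 makes the intent-to-treat analysis primary. It then warns that women who are non-adherent or stop the ring could depress safety rates, and for that reason says "additional analyses will be conducted on the per-protocol population, which will include only participants who were adherent to the protocol". The synopsis repeats this.

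**Protocol, adherence.** Section 8.4.2 names ring residuals and/or plasma and/or vaginal fluid levels as the measures and says "Participants will be categorized as either adherent or non-adherent, based on these measures". The levels that mark non-adherence are left to the SAP.

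**SAP, PP population.** Section 5.3 says "The PP (or protocol-adherent) population is a subset of the m-ITT population", restricted to women without major deviations. Its stated use is in 9.3.1: "This analysis (Analysis 1) will be performed on the m-ITT population, as well as on the PP population". In the shells, Table 14.3.7.5 carries the note "Please repeat the table for the PP population", and the figure list includes "Time to HIV-1 Seroconversion – PP population".

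**SAP, AE tables.** Tables 14.3.1.1 to 14.3.1.11 are all headed Safety Population. The repeats requested are by age and/or direct enrolment from IPM 027. For example, the note to Table 14.3.1.3 begins "Please repeat table for the following Subgroups: Age < 25 years".

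**SAP, ring residuals.** Section 9.2 takes a reported residual above 23.5 mg as a sign of non-adherence over one ring's use period. Table 14.3.5.2 tabulates residual bands with rings per trial month as the denominator.

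**SAP, declaration.** Section 11 reads "There are no changes to the protocol-planned analyses".

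**The concern.** Safety and adherence are the two primary endpoints, and Section 11 tells the reader that everything planned for them was kept.

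The protocol gives a specific reason for the PP analyses: dilution of safety rates by women not using the ring. A PP run of HIV-1 incidence does not address that. Without a PP version of the AE tables, the report cannot show whether the product-related AE proportions change when non-adherent women are set aside.

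The protocol's adherence classification is of participants. A table of rings per month cannot separate a few women who never used the ring from many women who each missed a single month. Those are different findings about a product meant for continuous use.

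**Working it through.** **1. Is the reviewed protocol text still in force?** SAP Appendix 6 says Amendment 1.0 is implemented in full and lists the Amendment 2.0 sections added to it. In the statistics chapter these are 8.4.5 and 8.5. Sections 8.4 to 8.4.2 are untouched.

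**2. Count of PP outputs.** From the SAP's list of tables and figures and the shells:

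| Output | In Safety population | Repeated in PP |
|---|---|---|
| AE tables 14.3.1.1 to 14.3.1.11 | 11 | 0 |
| Seroconversion Table 14.3.7.5 (Analysis 1) | – (m-ITT) | 1 |
| Kaplan-Meier Figure 14.3.7.8 | – (m-ITT counterpart is 14.3.7.7) | 1 |

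**3. Is any woman given a residual-based status?** Four places come near it:
- *Table 14.3.5.2:* counts rings per month.
- *Listing 16.2.5.1:* shows each woman's residuals but applies no rule.
- *SAP 9.2, last part:* summarises the last three or two rings of seroconverters against average residuals of HIV-negative women, as a visual comparison.
- *SAP 7.2:* labels a woman non-adherent for missed 3-monthly visits, which is not a dapivirine measure.

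None yields the classification in Protocol 8.4.2.

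**4. Why ring percentages do not give the share of women (illustration).** The documents give no rate, so assume q = 5% of rings exceed 23.5 mg. Take n = 12 rings per woman (monthly rings for up to 12 months, Protocol 3.2 and 6.4), all returned. For the share of women with at least one such ring:
- lowest, when the same women exceed it every month: q = 5%
- highest, when each affected woman has one such ring: n × q = 12 × 5% = 60%
- independent months: 1 − (1 − q)^n = 1 − 0.95^12 = 46.0%

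Schedules A and B in SAP 6.6 run longer. With 13 or 14 rings the highest values are 65% and 70%.

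A stricter rule reverses the picture. For at least six of 12 rings above the cut, independent months give about 0.001% of women, and full clustering gives 5%. The same ring table fits all of these.

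**5. Dilution of product-related AEs (illustration).** Assume a 5.0% risk in users, related AEs only in users, and a share s of women who never use the ring. The reported proportion is 5.0% × (1 − s):
- s = 5%: 4.75%
- s = 10%: 4.5%
- s = 20%: 4.0%

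Grade 3 or 4 AEs and serious AEs are counted whatever their cause, so this model does not apply to them.

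**The case against.** **The protocol's wording is loose.** Section 8.4 names no PP tables, 8.4.1 mentions no PP analysis, and 8.4 places HIV-1 seroconversion among secondary safety assessments, which does get a PP run. Section 8.4.2 promises no whole-trial status, and a monthly table with roughly one ring per woman is close to a monthly classing of women. This softens the point but does not remove it. The stated reason for the PP analyses is lowered safety rates, which points to AEs. And what 8.4.2 classifies is participants, whereas Table 14.3.5.2 counts rings.

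**The trial is descriptive and the dilution is small.** This stands. With the anticipated 1400 women, the exact 95% interval around 5.0% is 3.9% to 6.3%, and even the 20% non-user case (4.0%) falls inside it.

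**SAP 1 allows analyses it does not list.** True, but that neither delivers a planned analysis nor makes Section 11 correct.

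**Stronger readings that the documents do not support.** A reader might infer any of the following:
- *The SAP never looks at a woman's rings together.* It does so descriptively for seroconverters in 9.2. What is missing is a residual-based adherence status.
- *Unreturned rings are ignored.* SAP 9.4.1 and Table 14.6.1 report rings returned over rings dispensed. That figure mixes used and unused rings and is not crossed with residual level, so the gap is one of presentation.
- *The SAP's PP rules cannot be used for AEs.* SAP 7.2 removes inappropriately enrolled women entirely, and its censoring date could be applied to AE onset. The SAP simply does not say how.
- *Dropping plasma and vaginal fluid assays breaches 8.4.2.* The protocol's and/or wording permits ring residuals alone.

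**Conclusion.** Section 11 is wrong on two planned analyses of the primary endpoints: AE results in the PP population, and an adherent/non-adherent status for each woman based on dapivirine measures. This rests on comparing the texts and counting the shells, not on any assumed number.

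The practical size is unknown, because neither document gives a rate of non-use. Under the stated assumptions, the adherence gap could matter for interpretation (5% to 60% of women from one ring percentage), while the AE dilution is slight (5.0% to 4.75%). The Safety-population tables remain valid. A reader might infer that the reported safety profile is materially biased; the documents give no basis for that. The plan should be corrected, but the trial's main descriptive results do not fall with it.

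**What to change.** 1. **PP safety tables.** Repeat Tables 14.3.1.3 (product-related), 14.3.1.4 (Grade 3 or 4) and 14.3.1.5 (serious) in the PP population as supplementary tables. State how the SAP 7.2 censoring date applies to AE onset. Note that PP membership depends on behaviour after enrolment, so these tables are not a clean comparison. Note too that the listed PP criteria do not name ring residuals, so women who attend visits without using the ring can remain in the set.
2. **Per-woman residual summary.** Add the distribution, across women, of the share of each woman's assayed rings with a reported residual above 23.5 mg. This separates persistent from occasional non-use. Any single cut used to class women has no basis in the documents; label it the analysts' choice. If the database is already locked, label it post hoc. The virology addendum cites a main study report dated 09 April 2020, so this may well apply.
3. **Otherwise, correct Section 11** to declare and justify each planned analysis not done.
4. **Unreturned rings.** A cross-reference from Table 14.3.5.2 to Table 14.6.1 is enough.

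The cost is SAP wording, three reruns of existing tables and one new summary, all from data already collected. If only item 3 is taken up, it is a paragraph.
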